Despite the significant anti-tumor activity with Lu-PSMA RLT, there are several significant limitations of this approach as monotherapy: 1) There is significant **heterogeneity of PSMA expression**, both in analysis of individual circulating tumor cells as well as diagnostic PSMA PET imaging of metastatic lesions across individual patients, and 2) Within PSMA-avid lesions, there is a **limited duration of response**. In a recently presented prospective phase 2 study of Lu-PSMA, despite enriching for patients with more homogenous level of PSMA uptake on baseline PET imaging, the median PSA progression-free survival by PCWG criteria was only 6.3 months (95% CI 4.8 – 8.3), and median overall survival only 12.7 months. Nearly half of the 30 patients enrolled received less than the pre-specified 4 doses of Lu-PSMA treatment, for both toxicity-related reasons (hematologic, salivary gland) as well as rapid disease progression following initial response. The reasons for rapid disease progression include baseline heterogeneity of PSMA expression among disseminated tumor cells, leading to diffuse bone marrow involvement in a subset of patients. There is a clear and unmet medical need to merge the rapid anti-tumor responses achieved by Lu-PSMA RLT with a treatment that can both sustain and spread response to PSMA-negative lesions without excess cumulative toxicity.

Immune checkpoint inhibition, by virtue of antigen spread induced by immunogenic cell death induced by antecedent radioligand treatment, may accomplish this goal.

1.4 Immune Checkpoint Inhibition Leads to Durable Responses in a Minority of mCRPC Patients

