In **Part B** of the study, an additional 25 patients will be enrolled at the recommended phase 2 dose and schedule to obtain additional safety, efficacy, and immunologic data pertaining to the treatment combination.

Number of Subjects

Approximately 43 patients will be enrolled over an accrual period of approximately 18 months (N ~ 18 patients in Part A; 25 patients in Part B).

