5.2 Study Calendar: Schedule 1 (¹⁷⁷Lu-PSMA-617 prior to Pembrolizumab)

	Screening (Day -28 to -1 unless otherwise noted)	Treatment				End of Treatment	Safety Follow up			
		Cycle 1			Cycle 2+ (+/- 3 days unless otherwise noted)		D1 (+/- 3 days)	+ 21 days	30 Days (+/- 7 days) post-last dose	
		D1 (-3 days)	D2	D8 (+/- 1 day)						
Informed consent	x									
Medical history	x									
Baseline conditions	x									
Concurrent medications	x	x		x	x	x	x	x	x	
Height	x									
Weight	x	x		x	x	x	x	x	x	
ECOG Performance status	x	x		x	x	x	x	x	x	
Physical exam and vital signs	x	x		x	x	x	x	x	x	
CBC and Serum Chemistry Panel^{1,2}	x	x		x	x	x ³	x	x	x	
Thyroid function tests^{2,4}	x					x	x	x	x	
PSA²	x	x				x	x	x	x	
Testosterone	x									
⁶⁸Ga-PSMA-11 PET/CT or PET/MR	x ⁵						x			
Disease assessment	x					x	x			

¹ Chemistry panel to include: sodium, potassium, chloride, bicarbonate, BUN/creatinine, glucose, calcium, total bilirubin, AST, ALT, alkaline phosphatase

² Labs may be collected within a window of up to 3 days prior to each dose of pembrolizumab.

³ CBC + differential will be measured on C1D1, C1D8, C1D15, C2D1, C2D8, C2D15, Day 1 of C3+, and additionally as clinically indicated.

⁴ TSH (with reflex free T3/T4) testing to be performed during Screening, Cycle 2 Day 1, and Day 1 of every other cycle thereafter.

⁵ Allow for a 12-week window for the screening PSMA PET scan. PSMA PET at End of Treatment is optional.

	Screening (Day -28 to -1 unless otherwise noted)	Treatment				End of Treatment	Safety Follow up		
		Cycle 1			Cycle 2+ (+/- 3 days unless otherwise noted)		30 Days (+/- 7 days) post-last dose	90 Days (+/- 14 days) post last dose	
		D1 (-3 days)	D2	D8 (+/- 1 day)	D15 (+/- 1 day)	D1 (+/- 3 days)	+ 21 days		
(CT/MR, BS) ⁶									
Tumor Biopsy ⁷	x				x				
Whole blood for immune correlatives ⁸		x			x	x			
¹⁷⁷ Lu-PSMA-617 infusion		x							
SPECT/CT Dosimetry ⁹			x						
Normal Saline		x							
Anti-emetic pre-medication		x							
Pembrolizumab infusion					x				
AE assessment		x	x	x	x	x	x	x	x

⁶ Tumor assessment will be performed with CT chest/and/pelvis + whole body bone scan during Screening, C4D1 (-14d), C7D1 (-14d), and Day 1 (-14d) of every 4 cycles thereafter. If disease progression by RECIST 1.1/PCWG3, confirmatory scans are required \geq 4 weeks following first scan showing progression.

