8.4.2 Analytic Plan for Secondary Endpoints

Median duration of response

Median duration of response will be estimated using Kaplan-Meier product limit method, starting with the date of first scan indicating response until loss of response or progression, or death, whichever occurs first.

PSA response rate

The proportion of patients who achieve a greater than 50% decline from baseline PSA drawn on C1D1, at any point in the treatment course, will be descriptively reported along with 95% confidence interval.

PSA progression free survival

PSA progression will be defined using PCWG3 criteria. Median PSA progression free survival will be estimated using the Kaplan-Meier method. Duration will be measured from date of first treatment to date of first PSA meeting criteria for PSA progression.

Time to symptomatic skeletal related event

Symptomatic skeletal related event is defined as the first occurrence of one or more of the following: symptomatic fracture, surgery or radiation to bone, or spinal cord compression. The median time to symptomatic skeletal related event will be determined using Kaplan-Meier method.

Safety

The incidence and severity of adverse events related to study treatment will be descriptively reported using CTCAE v4.0.

Radiographic progression free survival and 6-month rPFS rate:

Radiographic progression of disease will be defined by RECIST v1.1 and PCWG3 criteria. For the first scheduled reassessment by bone scan (at Cycle 2), new bone lesions will require a confirmatory bone scan 6 or more weeks later. Median PFS will be estimated using the Kaplan-Meier method. Durations will be measured from the first day of study treatment (Cycle 1) to the first date of radiographic progression or death, whichever occurs first. Patients who discontinue study treatment for toxicity, withdraw from the study, or have PSA-only progression will be censored at the date of the last radiographic tumor assessment. Patients who discontinue treatment for clinical progression or deterioration will be included in the analysis.

Overall survival

Median overall survival and 95% confidence interval will be estimated using the Kaplan-Meier method. Duration will be measured from first date of study therapy to date of death from any cause.

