8.4.3 Analytic Plan for Correlative Endpoints

Lesion-specific response rate by baseline PSMA avidity on ⁶⁸Ga-PSMA-11 PET:

All target lesions on baseline cross-sectional imaging will be assessed for response (e.g. > 30% reduction in longest diameter) on subsequent imaging during the course of study. The median baseline uptake on Ga-PSMA-11 PET between responding versus non-responding lesions will be compared using Mann-Whitney test. In addition, Spearman's rank correlation will be used to compare baseline lesion uptake on Ga-PSMA-11 PET with percent change from baseline in longest tumor diameter on subsequent cross-sectional imaging on study.

Percent change from baseline in T cell repertoire, circulating T cell subsets, tumor infiltrating lymphocytes, and tumor PD-L1 expression by immunohistochemistry after one priming dose of Lu-PSMA RLT:

T cell repertoire will be estimated using Morasita's distance as previously described. Quantification of circulating T cell subsets and TILs will be performed using flow cytometry and immunohistochemical analysis of tumor tissue and whole blood, respectively. PD-L1 expression will be analyzed as the percentage of tumor cells with positive surface expression. Correlative testing may be performed at outside laboratory facilities (i.e. Strata Oncology). The percent change from baseline in these parameters will be reported using descriptive statistics (e.g. median, range, standard deviation). In an exploratory fashion, the study cohort will be dichotomized by those with percent change from baseline above and below median and efficacy outcomes will be compared between dichotomized subgroups using log-rank test for time-to-event endpoints (e.g. rPFS, duration of response) and Fisher's exact test for categorical variables (e.g. objective response rate, 6-month rPFS rate, PSA50 response rate).

Genomic Sequencing

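### The 6-month rPFS rate is to be compared between biomarker subgroups by Fisher's exact test, which has no place for patients censored before month 6

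*Combined protocol and SAP*

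**What the plan says.** Section 8.4.3 sets up the comparison: "In an exploratory fashion, the study cohort will be dichotomized by those with percent change from baseline above and below median". Efficacy outcomes are then compared between the two halves with a "log-rank test for time-to-event endpoints (e.g. rPFS, duration of response") and with Fisher's "exact test for categorical variables (e.g. objective response rate, 6-month rPFS rate, PSA50 response rate"). The same sentence therefore treats rPFS as a time-to-event endpoint and its 6-month rate as a yes/no variable.

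Section 8.4.2 defines rPFS from the first day of study treatment to radiographic progression or death. Patients who stop treatment for toxicity, "withdraw from the study, or have PSA-only progression will be censored at the date of the last radiographic tumor assessment". On estimation it says only "Median PFS will be estimated using the Kaplan-Meier method". The heading of that paragraph also covers the 6-month rate, but no estimator is named for it.

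Scans are due "during Screening, C4D1 (-14d), C7D1 (-14d), and Day 1 (-14d) of every 4 cycles thereafter" (section 5.2, with the same footnote in 5.3 and 5.4).

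**The concern.** Objective response and PSA50 are defined in sections 8.4.1 and 8.4.2 as simple proportions, so Fisher's test suits them. Six-month rPFS differs because the plan's own censoring rule can leave a patient's status at month 6 unknown. To fill a 2x2 table, the analyst must drop such patients, call them failures or call them successes. Each choice shifts the rate.

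Two things are at stake. The subgroup rates would be biased. And if the two biomarker halves differ in how much early censoring they have, a difference can appear where none exists. The halves are split on change in immune markers, which could be related to immune toxicity, itself a route to censoring. Because no convention is fixed, it could also be chosen after the data are seen.

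**Working it through.** The plan gives no power, alpha or expected rate for this comparison, so there is no stated figure to reproduce.

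**Can censoring fall before month 6?** With 21-day cycles, cycle k day 1 is study day (k − 1) × 21 + 1.

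- C4D1 = day 64 (week 9)
- C7D1 = day 127 (week 18)
- C11D1 = day 211 (week 30), with its window opening at day 211 − 14 = 197

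No scan is scheduled between about day 127 and day 197, and 6 months is about day 183. If censoring is placed at the last scan before the censoring reason, a reason arising between the week-18 and week-30 scans puts the censoring date near week 18.

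**Bias of the yes/no rate.** Assumptions, since the documents give none: exponential rPFS with true 6-month rate S = 0.50, independent exponential censoring, and a share q of patients censored before month 6.

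- Event hazard: λ = −ln(S)/6 = 0.1155 per month
- Censoring hazard c solves q = [c/(λ + c)] × [1 − exp(−6(λ + c))]
- Known event-free at month 6: F = exp(−6(λ + c))
- Observed event by month 6: E = [λ/(λ + c)] × (1 − F)
- Rate if censored are failures: F; if successes: 1 − E; if dropped: F/(F + E)

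For q = 0.20: c = 0.0530, λ + c = 0.1685, F = exp(−1.011) = 0.364, E = (0.1155/0.1685) × 0.636 = 0.436. This gives failures 0.364, successes 1 − 0.436 = 0.564, dropped 0.364/0.800 = 0.455.

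| Censored before month 6 | Dropped | Failures | Successes |
|---|---|---|---|
| 5% | 49.0% | 46.5% | 51.5% |
| 10% | 47.9% | 43.1% | 53.1% |
| 20% | 45.5% | 36.4% | 56.4% |
| 30% | 42.6% | 29.8% | 59.8% |

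The direction is the same for other true rates. At 20% censored, a true 30% becomes 25.1% / 20.1% / 40.1%, and a true 70% becomes 66.9% / 53.5% / 73.5%, in the same column order.

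**Effect on the test.** Section 3.1 gives the size: "Approximately 43 patients will be enrolled over an accrual period of approximately 18 months". A median split of 43 gives 21/22, and of the 25 in Part B gives 12/13. Simulation: 10,000 trials per setting, true rate 50% in both groups, two-sided 0.05 (assumed). False-positive rate of Fisher's test:

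| Patients | Censored by group | Dropped | Failures | Successes |
|---|---|---|---|---|
| 21/22 | 20% / 20% | 0.033 | 0.029 | 0.030 |
| 21/22 | 10% / 30% | 0.043 | 0.114 | 0.049 |
| 21/22 | 0% / 30% | 0.055 | 0.217 | 0.073 |
| 12/13 | 0% / 30% | 0.037 | 0.162 | 0.068 |

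The 0.114 follows from the first table: with censored patients as failures, the expected rates are 43.1% and 29.8%, which is 13.3 points apart with no true difference.

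**After the change.** The mean Kaplan-Meier 6-month estimate was 0.497 to 0.501 in every setting, and a subgroup comparison of Kaplan-Meier estimates at 6 months had a false-positive rate of 0.036 to 0.049. Both results assume independent censoring.

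**The case against.** The strongest reply is that little depends on this. The comparison is exploratory, has no alpha or decision rule, and sits beside a log-rank test of rPFS that does use censored times. That stands, and it sets the severity.

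A reader might infer that the censored group will be sizeable. The documents do not support this. Patients with PSA-only progression stay on treatment and keep being scanned (sections 3.4 and 5.1), so their last scan may come after month 6. Patients whose immune-related events force discontinuation remain in follow-up until progression or non-protocol therapy (section 4.8). Section 1.7.1 reports one DLT among 14 patients and no other Grade 3 or higher immune-related event. Against this, the Introduction reports for an earlier study of Lu-PSMA alone that "the median PSA progression-free survival by PCWG criteria was only 6.3 months", so PSA-only progression around month 6 is realistic. That was a different regimen, however, and it does not give a censored share. Whether section 8.4.2 means the last scan before the censoring reason or the last scan ever is not settled.

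A reader might also infer that the subgroup rates will contradict Kaplan-Meier 6-month rates reported elsewhere. Section 8.4.2 names Kaplan-Meier for the median only, so that mismatch cannot be asserted.

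Nor does a biased rate make the test invalid in every case. With 20% censored in both subgroups, Fisher's test stayed at about 0.03. Clear inflation needs unequal censoring, and arises mainly if censored patients count as failures.

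**Conclusion.** The point holds in a limited form. Fisher's test does not fit an endpoint that the plan itself censors, and no rule says how to classify a patient censored before month 6. The bias in the rate runs from at most 3.5 points at 5% censored (50% − 46.5%) to 20.2 points at 30% (50% − 29.8%). It is zero if nobody is censored before month 6. These sizes rest on an assumed true rate of 50% and independent exponential censoring. The false-positive figures also assume a two-sided 0.05 level and the stated group sizes.

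This is a minor point, and no primary or secondary conclusion changes.

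**What to change.** In section 8.4.3, remove the 6-month rPFS rate from the Fisher list and keep Fisher's test for objective response and PSA50. In 8.4.2, state that the 6-month rPFS rate is estimated by Kaplan-Meier with a confidence interval. Compare subgroups on those estimates (log-minus-log transformation, Greenwood variance), or rely on the log-rank test already planned. If Fisher's test is kept for this endpoint, state in advance how patients censored before month 6 are classified.

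The change does not remove every bias. Kaplan-Meier is unbiased only if censoring is unrelated to prognosis, which is doubtful for toxicity and PSA-only progression, so the report should say so.

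Cost: about one line of the SAP, with no new data, patients or visits. Free improvement.

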9.1 Pre-study Documentation

This study will be conducted in accordance with the ethical principles that have their origin in the Declaration of Helsinki as stated in 21 CFR §312.120(c)(4); consistent with GCP and all applicable regulatory requirements.

Before initiating this trial, the Investigator will have written and dated approval from the Institutional Review Board for the protocol, written informed consent form, subject recruitment materials, and any other written information to be provided to subjects before any protocol related procedures are performed on any subjects.

The clinical investigation will not begin until either FDA has determined that the study under the Investigational Drug Application (IND) is allowed to proceed or the Investigator has received a letter from FDA stating that the study is exempt from IND requirements.

The Investigator must comply with the applicable regulations in Title 21 of the Code of Federal Regulations (21 CFR §50, §54, and §312), GCP/ICH guidelines, and all applicable regulatory requirements. The IRB must comply with the regulations in 21 CFR §56 and applicable regulatory requirements.

9.2 Institutional Review Board Approval

The protocol, the proposed informed consent form, and all forms of participant information related to the study (e.g. advertisements used to recruit participants) will be reviewed and approved by the UCSF Institutional Review Board. Prior to obtaining IRB approval, the protocol must be approved by the Helen Diller Family Comprehensive Cancer Center Site Committee and by the Protocol Review Committee (PRC). The initial protocol and all protocol amendments must be approved by the IRB prior to implementation.

9.3 Informed Consent

All participants must be provided a consent form describing the study with sufficient information for each participant to make an informed decision regarding their participation. Participants must sign the IRB-approved informed consent form prior to participation in any study specific

procedure. The participant must receive a copy of the signed and dated consent document. The original signed copy of the consent document must be retained in the medical record or research file.

9.4 Changes in the Protocol

Once the protocol has been approved by the IRB, any changes to the protocol must be documented in the form of an amendment. The amendment must be signed by the Investigator and approved by PRC and the IRB prior to implementation.

If it becomes necessary to alter the protocol to eliminate an immediate hazard to patients, an amendment may be implemented prior to IRB approval. In this circumstance, however, the Investigator must then notify the IRB in writing within five (5) working days after implementation. The Study Chair and the UCSF study team will be responsible for updating any participating sites.

10 Protection of Human Subjects

10.1 Protection from Unnecessary Harm

Each clinical site is responsible for protecting all subjects involved in human experimentation. This is accomplished through the IRB mechanism and the process of informed consent. The IRB reviews all proposed studies involving human experimentation and ensures that the subject's rights and welfare are protected and that the potential benefits and/or the importance of the knowledge to be gained outweigh the risks to the individual. The IRB also reviews the informed consent document associated with each study in order to ensure that the consent document accurately and clearly communicates the nature of the research to be done and its associated risks and benefits.

Appendix 1 Performance Status Criteria

ECOG Performance Status Scale		Karnofsky Performance Scale	
Grade	Descriptions	Percent	Description
0	Normal activity Fully active, able to carry on all pre-disease performance without restriction	100	Normal, no complaints, no evidence of disease
		90	Able to carry on normal activity; minor signs or symptoms of disease
1	Symptoms, but ambulatory Restricted in physically strenuous activity, but ambulatory and able to carry out work of a light or sedentary nature (e.g., light housework, office work)	80	Normal activity with effort; some signs or symptoms of disease
		70	Cares for self, unable to carry on normal activity or to do active work
2	In bed < 50% of the time Ambulatory and capable of all self-care, but unable to carry out any work activities Up and about more than 50% of waking hours	60	Requires occasional assistance, but is able to care for most of his/her needs
		50	Requires considerable assistance and frequent medical care
3	In bed > 50% of the time Capable of only limited self-care, confined to bed or chair more than 50% of waking hours	40	Disabled, requires special care and assistance
		30	Severely disabled, hospitalization indicated Death not imminent
4	100% bedridden Completely disabled Cannot carry on any self-care Totally confined to bed or chair	20	Very sick, hospitalization indicated Death not imminent
		10	Moribund, fatal processes progressing rapidly
5	Dead	0	Dead

Appendix 2 Data and Safety Monitoring Plan for a Phase 1 Study

The UCSF Helen Diller Family Comprehensive Cancer Center (HDFCCC) Data and Safety Monitoring Committee (DSMC) is responsible for monitoring data quality and subject safety for all HDFCCC institutional clinical studies. A summary of DSMC activities for this study include:

- Review of subject data
- Review of suspected adverse reactions considered “serious”
- Monitoring every six months (depending on study accrual)
- Minimum of a yearly regulatory audit

Monitoring and Reporting Guidelines

Investigators will conduct continuous review of data and subject safety and discuss each subject's treatment at monthly Site Committee meetings. These discussions are documented in the Site Committee meeting minutes. The discussion will include the number of subjects, significant toxicities in accordance with the protocol, and observed responses.

All institutional Phase 2 or 3 studies are designated with a moderate risk assessment. The data is monitored twice per year with twenty percent of the subjects monitored (or at least three subjects if the calculated value is less than three).

Adverse Event Review and Monitoring

All grade(s) 3-5 adverse events, whether or not unexpected, and whether or not considered to be associated with the use of the study drug, will be entered into OnCore®, UCSF's Clinical Trial Management System.

All grade(s) 3-5 adverse events entered into OnCore® will be reviewed on a monthly basis at the Site Committee meetings. The Site Committee will review and discuss the selected toxicity, the toxicity grade, and the attribution of relationship of the adverse event to the administration of the study drug(s).

In addition, all suspected adverse reactions considered “serious” entered into OnCore®, will be reviewed and monitored by the Data and Safety Monitoring Committee on an ongoing basis and discussed at DSMC meetings, which take place every six weeks.

If a death occurs during the treatment phase of the study or within 30 days after the last administration of the study drug(s) and it is determined to be related either to the study drug(s) or to a study procedure, the Investigator or his/her designee must notify the DSMC Chair within **1 business day** of knowledge of this event. The contact may be by phone or e-mail.

Increase in Adverse Event Rates

